4.0 Test Schedule

Tests and procedures	Active Monitoring Phase				
	Baseline <14 days of Registration	Prior to each new cycle ¹⁰ <= 3 days (starting at cycle 2)	Restaging End of Cycle 8 (6-8 Weeks after Day 1 of Cycle 8)	End of Treatment if discontinued early (at PD or PMD, withdrawal, or removal)	Observation (Every 30 days x 90 days, , then every 90 days x 2.5 years, then every 6 months until 5 years from registration) +/-14Days
History and exam	X	X ¹	X	X	X
B Symptoms ⁹	X	X	X	X	X
ECOG PS	X	X	X	X	X
Height (baseline only), Weight	X	X	X	X	X
Adverse event assessment	X	X	X	X	X
Cardiac ejection fraction	X ¹⁴				
ECG	X				
Pulmonary function studies (including oxygen saturation) ¹²	X				
HBV sAg and HCV Ab or HCV RNA	X				
Comprehensive metabolic panel: (ALT, AST, total bilirubin, alkaline phosphatase), BUN or serum urea level, creatinine, Ca, Mg, Na, K, Cl, LDH, Glucose, amylase, lipase, Albumin, bicarbonate	X ⁴	X	X	X	
INR ^{K, 13}		X	X	X	X
TSH (with Free T4 and Free T3)	X ⁴	X ¹¹	X	X	
Hematology: CBC/differential	X ⁴	X	X	X	X
Erythrocyte sedimentation rate	X				
Uric Acid	X				
Pregnancy Test ³	X	X	X	X	X
PET-CT	X ¹⁴	X ²	X	X	
CT scan Chest/Abd/Pelvis					X ⁵
Mandatory Research blood samples (See section 14.0) ^{K, 6}		X ¹⁵	X	X	X ⁸
Mandatory Tissue sample ^{7, K}	X				

(Footnotes on next page)

- 1 If on physical exam there are any palpable lymph nodes present: Tumor (bidimensional)-measurements by physical exam to be done at end of every cycle, prior to next cycle.
- 2 End of cycle 2, prior to Cycle 3 (≤ 5 days)
- 3 For women of childbearing potential only. A serum or urine pregnancy testing is required ≤ 24 hours before registration, then every other cycle. (more frequently if required by local standard). After discontinuation from nivolumab, these should be repeated at approximately 30 days and approximately 70 days [or more frequently if required by local standard].
- 4 Must be obtained ≤ 7 days prior to registration.
- 5 CT scan is every 3 months during the first year of observation, then as clinically indicated.
- 6 Must be drawn on Day 1 of each cycle before treatment Cycles 1-8, at restaging 6-8 weeks post Cycle 8 Day 1, end of treatment if discontinued early (PD or PMD, withdrawal or removal), and at time of PD or PMD.
- 7 To be submitted within ≤ 14 days following Registration; see 17.0 Pathology Considerations/Tissue Biospecimens
- 8 Only at time of PD or PMD

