14.0 Body Fluid Biospecimens

14.1 Summary Table of Research Blood/Blood Products to Be Collected for This Protocol

Indicate if specimen is mandatory or optional	Collection tube description and/or additive (color of tube top)	Volume to collect per tube (number of tubes to be collected)	Blood product being processed and submitted by participating site	Cycles 1-8 Day 1 Pre-treatment	6-8 weeks after Day 1 of Cycle 8	End of Treatment, If discontinued early (At PMD or PD, withdrawal or removal)	At time of PMD or PD	Additional processing required at site after blood draw?	Storage /shipping conditions¹
Mandatory	SST (Marble top)	8.5 ml (1)	Whole blood	X	X	X	X	No	Refrigerated / Do not Freeze
Mandatory	EDTA (purple top)	10 mL (2)	Whole blood	X	X	X	X	No	Refrigerated / Do not Freeze

After all samples have been processed according to kit instructions, ship all specimens according to shipping instructions (see below for detailed shipping instructions.)

14.2 **Kits will be used for this study** and will be contain supplies for collecting, processing and shipping specimens.

14.21 Participating institutions may obtain kits by e-mailing [REDACTED] [REDACTED] E-mail requests should include the site address, contact information and number of kits being requested.

14.22 Kits will be sent via FedEx® Ground at no additional cost to the participating institutions. Please allow 3 to 4 business days to receive the kits.

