- 16.322 Duration of response is defined for all evaluable patients who have achieved a response as the date at which the patient's objective status is first noted to be a CMR or PMR to the earliest date progression (PMD or PD) is documented. If a patient has not had disease progression, they will be censored on the date of their last disease assessment. The distribution of duration of response will be estimated using the method of Kaplan-Meier.
- 16.322 Progression-free survival is defined as the time from registration to the earliest date of documentation of disease progression (PMD or PD) or death due to any cause. If a patient is alive and has not had disease progression, they will be censored on the date of their last disease assessment. The distribution of progression-free survival will be estimated using the method of Kaplan-Meier.
- 16.323 Overall survival time is defined as the time from registration to death due to any cause. If a patient is still alive, they will be censored on the date of their last follow-up. The distribution of overall survival will be estimated using the method of Kaplan-Meier.
- 16.324 Adverse Events: All eligible patients that have initiated treatment will be considered evaluable for assessing adverse event rate(s). Adverse events will be assessed using CTCAE version 4.0 per Section 10.0. The maximum grade for each type of adverse event will be recorded for each patient, and frequency tables will be reviewed to determine patterns. Additionally, the relationship of the adverse event(s) to the study treatment will be taken into consideration.
- 16.33 Correlative Outcome Analyses: Due to the small overall sample size, the results of these analyses will be considered exploratory and hypothesis-generating in nature.
- 16.331 Biomarkers including intratumoral cell populations, genetic variability, serum cytokines, and T-cell activation will be evaluated both before and during treatment. Baseline values and changes in these parameters over time will be both graphically

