and quantitatively summarized and explored. Standard paired comparisons methodologies (paired t-tests, Wilcoxon signed rank tests and Fisher's exact tests for interval, ordinal and nominal level data, respectively) will be used to assess changes in these variables before and after therapy. In addition, baseline values and changes over time in each measure will be explored in relation to clinical outcome to explore any differences between responders and non-responders and by depth of response (CMR vs. PMR) to identify potential biomarkers.

- 16.4 Early Safety Analysis: An early safety analysis will be performed after the first 6 patients have been accrued to the study at dose level 1 and observed for one cycle. If 2 or more of the first 6 patients experience a DLT as defined in Section 7.12, then the starting dose level will be adjusted and additional cohorts may be evaluated at dose levels -1 and -2 as described below. Accrual will be halted while evaluating each cohort in the early safety analysis.
- 16.41 Dose level +1: Six evaluable patients will be accrued onto dose level +1 and observed until they complete one cycle treatment. If 0 or 1 out of 6 patients experience a DLT, accrual will continue in the phase II portion at dose level 1. If 2 or more patients experience a DLT on dose level +1, the toxicity level for dose level +1 will be considered unacceptable and six additional patients will be treated on dose level -1.
- 16.42 Dose de-escalation to Dose level -1: If dose level +1 has an unacceptable level of toxicity, six evaluable patients will be accrued onto dose level -1. If 0 or 1 out of 6 patients experience a DLT on dose level -1, accrual will continue in the phase II portion at dose level -1. If 2 or more patients experience a DLT, the toxicity level for dose level -1 will be considered unacceptable and six additional patients will be treated on dose level -2.
- 16.43 Dose escalation to Dose level -2: If dose level -1 has an unacceptable level of toxicity, six evaluable patients will be accrued onto dose level -2. If 0 or 1 out of 6 patients experience a DLT on dose level -2, accrual will continue in the phase II portion at dose level -2. If 2 or more patients experience a DLT, the toxicity level for dose level -2 will be considered unacceptable and accrual to the study will be temporarily closed, evaluated and potentially amended.
- 16.5 Data & Safety Monitoring:

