17.1 Tissue Biospecimen Submission

17.11 Summary Table of Tissue Biospecimens for This Protocol

Type of tissue biospecimen to submit	Mandatory or optional	When to submit	Reason for submission (background/methodology section)	Where to find specific details for biospecimen submission
Formalin-fixed paraffin-embedded (FFPE) tissue blocks with corresponding H&E (OR (10) 5 micron unstained slides with corresponding H&E)**	Mandatory	Within ≤14 days following registration	Correlative biomarkers, tumor genetic variability and Banking	Section 17.31

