17.2 Paraffin Embedded Tissue Blocks/Slides

17.3 Submit one formalin fixed paraffin-embedded (FFPE) tissue block Biopsy material obtained at the time of recurrence is preferred, but if not available, biopsy material obtained at the time of initial diagnosis of Hodgkin Lymphoma may be submitted *OR* Please submit biopsy material from each surgery.) **A corresponding H&E slide for each submitted block must be provided** to permit quality assessment of each tissue block.

17.31 The FFPE tissue block is preferred; however, **if an institution is unable to provide a tissue block**, cut (11) 5 micron unstained slides and mount on charged glass slides. **Label the slides with ACCRU patient ID number, accession number, and order of sections.** H&E stain the first slide (i.e., slides labeled 1, 11, etc.). These H&E slides will be reviewed centrally under the research base’s protocol for assessing tissue quality. **Do not bake or place covers slips on the slides.**

17.32 The following materials below are mandatory and required for shipment:

- Paraffin embedded tissue blocks with corresponding H&E slide (OR (10) 5 micron unstained slides with corresponding H&E(s)).

17.33 [Redacted] to notify Mayo Clinic Reference Laboratory when the specimen(s) are being shipped.

17.34 Specimens should be shipped to the following address:

[Redacted]
[Redacted]
[Redacted]
[Redacted]
[Redacted]

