17.4 Tumor Assays

17.41 **Immunohistochemistry (IHC):** Previous studies of tumor biomarkers have shown that the tumor microenvironment in Hodgkin lymphoma is very important. These studies have shown that the number, phenotype and distribution of intratumoral immune cells predicts response to therapy. To confirm the prognostic or predictive role of immune cells in patients with Hodgkin lymphoma treated with brentuximab vedotin and nivolumab, we will use submitted paraffin-embedded tissue to measure the T-cell and macrophage infiltrate and correlate cell numbers and location with patient response and progression – free survival. As described above, serial 5- μ m paraffin-embedded sections will be used for IHC. The tissue will be deparaffinized with three changes of xylene and cleared through graded series of ethanol. Endogenous peroxidase will be quenched by incubation in 50% methanol/H₂O₂ and after rinsing with tap water; all sections will be pretreated for 30 minutes with 50 mmol/L EDTA using a steamer and cooled for additional 5 minutes.

All staining will be done automatically on DAKO Autostainer using the following antibodies to CD11c (Leica Microsystems 5D11), CD14 (Cell Marque EPR 3653), CD163 (DAKO 1F8), CD68 (DAKO PG-M1), CXCL13 (R&D Systems 53610), FOXP3 (Abcam 236AE/7), CD3 (R&D Systems), PD-L1 (405.9A11), PD-L2 (366C.9E5) and PD-1 (Abcam NAT). The sections will be viewed with an Olympus BXFA51 microscope and pictures taken with an Olympus DP71 camera.

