17.42 **Fluorescence in situ hybridization (FISH):** FISH will be performed on Hodgkin lymphoma tissue sections to assess copy number on chromosome 9p24.1. The bacterial artificial chromosome probes (CHORI; www.chori.org) RP11-599H2O, which maps to 9p24.1 and includes *CD274* (encoding PD-L1, labeled with Spectrum Orange), and RP11-635N21, which also maps to 9p24.1 and includes *PDCD1LG2* (encoding PD-L2, labeled with Spectrum Green), will be cohybridized. A control centromeric probe, Spectrum Aqua-labeled *CEP9* (Abbott Molecular) that maps to 9p11-q11, will be hybridized according to the manufacturer's recommendations. Malignant Reed–Sternberg cells will be identified by means of nuclear morphologic features, and all such cells will be analyzed. Nuclei with a target:control probe ratio of at least 3:1 will be classified as amplified, those with a probe ratio of more than 1:1 but less than 3:1 will be classified as relative copy gain, and those with a probe ratio of 1:1 but with more than two copies of each probe will be classified as polysomic for chromosome 9p.

17.43 **Molecular Signature:** We will define the intratumoral molecular signature predictive of response to therapy in patients with Hodgkin lymphoma. We will use a previously described gene expression profile and optimize it for use in paraffin-embedded tissue [Sriedl et al]. The coefficients and the capture-based hybridization pipeline designed for formalin-fixed, paraffin-embedded tissues (FFPET) will be used. The genes include *CSFR1*, *PD-L1*, *PD-L2*, *EZH2*, *MEF2B*, *ARID1A*, *CARD11*, *FOXO1*, *CREBBP* and *EP300*. In addition, gene signatures downstream of specific mutations will be explored using a paraffin-based approach that follows gene set enrichment analysis of mutated cases. The signature(s) will be used to explore their ability to select cases with inferior outcomes.

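### Section 16.331 uses an unpaired test (Fisher's exact) for before/after change in nominal biomarkers and promises on-treatment tissue evaluation with only one tissue sample scheduled

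*Combined protocol and SAP*

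**What the plan says.** **Test.** Section 16.331 presents the paired t-test, the Wilcoxon signed rank test and Fisher's exact test together as standard methods for paired comparisons. The sentence ends: "Fisher's exact tests for interval, ordinal and nominal level data, respectively) will be used to assess changes in these variables before and after therapy". The word *respectively* ties Fisher's exact test to nominal data. The next sentence adds comparisons of responders with non-responders and of CMR with PMR, and names no test for them.

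**Timing.** Section 16.331 also states: "Biomarkers including intratumoral cell populations, genetic variability, serum cytokines, and T-cell activation will be evaluated both before and during treatment".

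**Tissue sampling.** The Section 4.0 test schedule marks tissue once, in the baseline column, and footnote 7 reads "To be submitted within ≤ 14 days following Registration". The Section 17.11 table gives the same single time: "Within ≤14 days following registration". Section 17.3 asks for one block, prefers material from recurrence, and adds "Please submit biopsy material from each surgery".

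**Planned use of tissue.** Section 17.41 will "measure the T-cell and macrophage infiltrate and correlate cell numbers and location with patient response and progression"-free survival. Section 17.42 grades FISH results by nucleus: "Nuclei with a target:control probe ratio of at least 3:1 will be classified as amplified".

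**Blood sampling.** Research blood is serial. Section 14.1 lists "Cycles 1-8 Day 1 Pre-treatment", then restaging, early end of treatment, and progression.

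**Status.** Section 16.33 labels all these analyses exploratory, and goal 2.31 says the T-cell and cytokine results will be reported descriptively.

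**The concern.** Each patient supplies both the before and the after value, so the two are correlated, and a test of change has to use the pairs. The first two tests in the list do so. Fisher's exact test does not, and the plan does not say how it would be applied to paired data. An analyst following the text could do either of two things, and neither properly tests within-patient change.

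Separately, if tissue is taken once, no during-treatment value of an intratumoral marker exists, so the change that Section 16.331 describes cannot be computed for it.

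At stake is the reading of exploratory biomarker results. A real change in a categorised blood marker could be missed, or stability within patients could be reported as change. The tissue-change analysis would have no data behind it.

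**Working it through.** The plan gives no sample size, power or significance level for these analyses, so it has no figure of its own to reproduce. The number of patients, 56, is the evaluable sample in Section 16.2. All counts, rates and correlations below, complete pairs, and the two-sided 0.05 level are assumptions.

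**Notation.** Of *n* patients, *a* are positive at both times, *b* revert (positive to negative), *c* convert (negative to positive), and *d* are negative at both times.

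- Exact McNemar: p = 2 × Σ C(b+c, k) / 2^(b+c), summed over k from 0 to min(b, c), capped at 1.
- Fisher, use (i): the table of (a+b) of *n* positive before against (a+c) of *n* positive after, as if these were separate groups.
- Fisher, use (ii): the table with cells a, b, c, d, which tests whether before and after are associated.

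**Use (i), n = 56, a = 14, b = 0, c = 6, d = 36.** Positive: 14 before, 20 after.

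- McNemar: 2 × 1/2^6 = 2/64 = 0.031.
- Fisher on 14/56 versus 20/56: p = 0.30.

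**Use (i), 40 complete pairs, a = 10, b = 0, c = 6, d = 24.** McNemar is again 0.031. Fisher on 10/40 versus 16/40 gives p = 0.23.

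**Sensitivity to reversions, same margins (14 to 20 of 56).** Fisher stays at 0.30.

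- 7 convert, 1 reverts: McNemar 2 × (1 + 8)/256 = 0.070.
- 8 convert, 2 revert: McNemar 2 × (1 + 10 + 45)/1024 = 0.109.

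The contrast across 0.05 therefore rests on there being no reversions.

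**Use (ii), n = 56, a = 14, b = c = 0, d = 42.** Nobody changes. McNemar p = 1. Fisher on the cross-table gives 1/C(56, 14) = 1.7 × 10⁻¹³. The small p-value reflects only that patients stay as they were.

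**Power for use (i).** Exact enumeration, n = 56, positives rising from 25% to 40%. The within-patient correlation is phi = (P(both) − 0.25 × 0.40) / √(0.25 × 0.75 × 0.40 × 0.60), with denominator 0.212.

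| P(both) | P(revert) | P(convert) | phi | Fisher | McNemar |
|---|---|---|---|---|---|
| 0.22 | 0.03 | 0.18 | 0.57 | 0.25 | 0.63 |
| 0.18 | 0.07 | 0.22 | 0.38 | 0.29 | 0.48 |
| 0.15 | 0.10 | 0.25 | 0.24 | 0.31 | 0.40 |
| 0.10 | 0.15 | 0.30 | 0 | 0.33 | 0.31 |

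**False-positive rate.** Simulation, 20,000 data sets, n = 56, 50% positive at both times (no net change), correlation 0.5. Rejection at 0.05: use (i) 0.2%, use (ii) 95.7%, McNemar 2.5%.

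**Sampling against analysis.** The statement about evaluation before and during treatment covers four marker families.

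- *Intratumoral cells:* measured by IHC on the submitted tissue (17.41). There is one scheduled sample and no during-treatment value.
- *FISH classes:* the clearest nominal marker, but on tissue only and assigned to nuclei rather than patients (17.42).
- *Serum cytokines and flow cytometry:* on blood and quantitative (14.511, 14.512), so the paired t-test or signed rank test applies.
- *Blood DNA:* Section 14.5 says it is banked, with no specific genetic test performed.

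The wrong test name therefore takes effect only if a serial blood marker is analysed as categories. The tissue mismatch needs no such condition.

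**The case against.** The strongest reply is that nothing planned would change. No nominal marker is measured serially, the blood assays fall under the two tests that are correctly named, and the work is exploratory with no decision attached. The example with six conversions and no reversions is also favourable: six is the smallest number of discordant pairs at which exact McNemar can fall below 0.05. On tissue, Sections 14 and 17 already separate serial blood from one-time tissue, so the timing sentence can be read as loose wording. The recurrence and each-surgery wording in 17.3 might even allow a later sample.

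Much of this stands. It sets the low rating, and the p-values should not be read as an expected loss in this trial. It does not make Fisher's exact test a paired test, and no other section corrects the wording. Reading Fisher as meant for responder versus non-responder comparisons does not fit the text, because those come in a separate sentence. Section 17.3 sets no on-treatment time point.

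One further point stands. Section 14.511 says cytokines are measured in pre-treatment samples. That could mean baseline only or each cycle's pre-dose draw, and it decides whether cytokine change can be computed.

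**Conclusion.** The concern holds, as a minor point. Fisher's exact test is wrongly named for paired nominal data, and the promised during-treatment evaluation of intratumoral cells has no scheduled sample behind it.

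The first error matters only if a serial blood marker is categorised. Under the assumed 25% to 40% shift in 56 patients, treating the two times as separate groups gives power of 0.25 against 0.63 at a correlation of 0.57, with no loss at zero correlation. Using the before-by-after table instead answers a different question altogether. The second point rests on the schedule alone and needs no assumption.

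The primary and secondary endpoints, the sample size and the decision rules are unaffected.

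**What to change.** Amend Section 16.331 as follows:

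- For before/after change in nominal markers, name the exact McNemar test for two categories and Bowker's test for more than two. If the question is change in category proportions rather than symmetry, a test of marginal homogeneity is more direct.
- Keep Fisher's exact test for responder versus non-responder and CMR versus PMR comparisons.
- Limit before/after analyses to markers from the serial blood draws in Section 14.1.
- Analyse tissue markers, including tumour genetic variability, at baseline only, against response and PFS, as Section 17.41 already plans for IHC.

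It would help to state in Section 14.511 whether cytokines are measured at baseline only or at each Day 1 draw.

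The cost is about two sentences in 16.331 and a clarifying phrase in 14.511, with no added samples, assays or procedures for the changes to 16.331.

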2.0 Goals

2.1 Primary

2.11 The primary objective of the study is to determine the efficacy based on overall metabolic response rate (PMR + CMR) of Brentuximab Vedotin /Nivolumab in previously untreated Hodgkin Lymphoma patients 60 years of age or older, or those considered unsuitable for standard chemotherapy because of a low cardiac ejection fraction (<50%) or impaired pulmonary or renal function.

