7.11 Safety Analysis Dose Levels

Dose level	Brentuximab Vedotin	Nivolumab
-2	1.2 mg/kg IV Day 1	Omit
-1	1.8 mg/kg IV Day 1	Omit
*1	1.8 mg/kg IV Day 1	3 mg/kg IV Day 1

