16.0 Statistical Considerations and Methodology

16.1 Overview

This is a phase II study of nivolumab and brentuximab vedotin in patients with untreated Hodgkin lymphoma ≥ 60 years old or under 60 and unable to receive standard ABVD chemotherapy. The study is designed to assess the overall metabolic response rate using a single stage phase II study design with an interim analysis. Accrual will be halted after 6 patients to assess safety (see Section 16.4). We do not plan to halt accrual during the interim analysis (see Section 16.214).

16.11 Primary Endpoint: The primary endpoint of this trial is the rate of overall metabolic response. A metabolic response is defined as a patient who has achieved an objective status of PMR or CMR at the end of cycle 8. Throughout Section 16.0, metabolic response will be considered synonymous with “success”, unless specified otherwise. All patients meeting the eligibility criteria, who have signed a consent form and have begun treatment will be evaluable for response, unless they are determined to be a major violation or are replaced in the safety analysis phase per Section 13.6. If the safety analysis determines that a reduction to the starting dose is warranted, only patients treated at the final dose level will be included when evaluating the decision rules in Sections 16.211 and 16.212. Patients treated at other dose levels will be summarized separately.

16.2 Statistical Design:

16.21 Decision Rule:

In a single-agent front-line phase II study of HL patients ≥ 60 years-old treated with brentuximab vendotin, the interim analysis of 27 patients reported rate of 93%⁶. This study will look at responses maintained until the end of cycle 8 and will utilize an updated response criteria that assesses metabolic response (Cheson 2014). Considering these factors, along with heterogeneity of disease in patients with HL and a broader eligibility criteria that includes patients < 60 years old with other co-morbidities, an overall metabolic response rate of greater than 65% for brentuximab vendotin with the addition of nivolumab would be of interest for this study.

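### If the safety lead-in drops nivolumab, does the plan leave open which treatment its primary conclusion is about?

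*Combined protocol and SAP*

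**What the plan says.** The primary objective (Section 2.11) is "efficacy based on overall metabolic response rate (PMR + CMR) of Brentuximab Vedotin /Nivolumab in previously untreated Hodgkin Lymphoma patients", and the overview in 16.1 opens in the same sense: "This is a phase II study of nivolumab and brentuximab vedotin in patients with untreated Hodgkin lymphoma".

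The table headed "7.11 Safety Analysis Dose Levels" has three rows. Level 1, the starting level, contains both drugs. Levels -1 and -2 contain brentuximab vedotin only, with nivolumab marked as omitted.

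Section 16.41 assesses six patients at level 1, which it calls +1. With 0 or 1 DLT, "accrual will continue in the phase II portion at dose level 1". With 2 or more, the toxicity of that level is deemed unacceptable and six further patients are treated at level -1. Sections 16.42 and 16.43 repeat the pattern. If level -2 is reached and tolerated, "accrual will continue in the phase II portion at dose level -2". Section 16.4 adds: "Accrual will be halted while evaluating each cohort in the early safety analysis".

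If the starting dose is reduced, 16.11 and 16.311 confine the decision rules in 16.211 and 16.212 to patients at the final dose level and report the other levels apart. Those rules give a verdict on *this regimen* or *the treatment*.

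The benchmark in 16.21 starts from a single-agent study in older patients, "treated with brentuximab vendotin, the interim analysis of 27 patients reported rate of 93" per cent, and concludes that "an overall metabolic response rate of greater than 65% for brentuximab vendotin with the addition of nivolumab would be of interest".

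**The concern.** Stepping down from level 1 changes the regimen, because it removes a drug. On that branch none of the 25 to 56 patients in the primary test was assigned the combination named in 2.11 and 16.1. The rules still return a verdict in the same words, with the same 65% and 80%, and no sentence says that the verdict is then about one drug only.

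If a reader took it as a verdict on the combination, a positive result would credit nivolumab with activity seen without it, and a negative one would condemn a combination that the test never examined. The six level 1 patients are too few to answer 2.11 themselves.

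**Working it through.** **1. The plan's own figures.** Inputs from 16.211 and 16.212: stop if 17 or fewer of 25 respond; declare promise if at least 41 of 56 respond. With true success rate p:

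- P(stop) = P(X1 ≤ 17), X1 ~ Bin(25, p)
- P(declare) = sum over x = 18 to 25 of P(X1 = x) × P(X2 ≥ 41 − x), X2 ~ Bin(31, p)

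| p | P(declare) | Table in 16.24 | P(stop) | Table in 16.24 |
|---|---|---|---|---|
| 0.65 | 0.097 | 0.10 | 0.694 | 0.69 |
| 0.70 | 0.293 | 0.29 | 0.488 | 0.49 |
| 0.75 | 0.593 | 0.59 | 0.273 | 0.27 |
| 0.80 | 0.852 | 0.85 | 0.109 | 0.11 |

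The table is reproduced. These probabilities depend only on p, so they hold for whichever single regimen supplies the patients. Sections 16.11 and 16.311 carry both rules to the final level, so the interim stop stays in force there without further wording. That matters, because 41 of 56 used alone would have a type I error of 0.124.

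**2. How often the branch is reached.** P(2 or more DLTs in 6) = 1 − (1 − q)^6 − 6q(1 − q)^5. At q = 0.10 this is 1 − 0.5314 − 0.3543 = 0.114.

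| Assumed DLT rate q | 5% | 7% | 10% | 14.8% | 20% | 30% |
|---|---|---|---|---|---|---|
| P(leave level 1) | 0.033 | 0.061 | 0.114 | 0.219 | 0.345 | 0.580 |

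The documents give no DLT rate for the combination, so every q is an assumption. The 7% is the grade 4 neutropenia rate on single-agent brentuximab vedotin (Section 1.225). The 14.8% is the exact 95% upper limit, 1 − 0.025^(1/23), for no grade 4 or 5 events in 23 patients on nivolumab (Section 1.1). Both come from relapsed disease and neither is limited to cycle 1, as the DLT definition is.

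**3. Could another analysis set answer 2.11?** Six patients cannot: the exact 95% intervals for 4, 5 and 6 responders of 6 are 22% to 96%, 36% to 99.6% and 54% to 100%. Pooling level 1 with a full set at level -1 would give 6 / (6 + 56) = 10% of patients assigned the combination and would mix two regimens. Restricting the rule to the final level is therefore the right population, and no wording would recover an answer to 2.11.

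**4. What the verdict refers to.** Reading the sections together:

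- 7.11 states what each level contains.
- 16.11 and 16.311 tie the rules to the final level and keep the others apart.
- 16.41 has already judged the only combination level unacceptably toxic. A recommendation for further testing under 16.212 cannot sensibly mean that regimen.

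Only one reading is left: the regimen at the final level.

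**5. Does 65% carry over?** The only response rate cited in 16.21 is for brentuximab vedotin alone. The reasons for setting the bar lower are response held to the end of cycle 8, metabolic criteria, disease heterogeneity and wider eligibility. None of them depends on nivolumab. The null is at least as well supported for the single agent as for the combination.

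**The case for a change.** The best case for a change is textual. Section 16.21 states its benchmark for the combination, and 2.11 is never qualified. Section 16.43 foresees evaluation and possible amendment only if level -2 also fails, so at a tolerated -1 or -2 accrual simply resumes under the same rule. If brentuximab vedotin alone had an assumed true rate of 80% or 85%, the rule would declare promise with probability 0.85 or 0.97, with no nivolumab assigned to anyone in the test. Because the combination was untested (Section 7.1), the branch is a planned possibility, and a planned branch deserves a planned interpretation. One could also ask for 65% and 80% to be confirmed before accrual at a reduced level, with estimation only if they are not.

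Part of this stands. No sentence names the referent or says that 2.11 would go unanswered, and one line saying so would do no harm. The rest does not require a change. A positive result at a true 80% or 85% would be a correct statement about the drug that was given. Re-confirming the thresholds is a matter of preference when the null already rests on single-agent data and the type I error is intact. The accrual halt in 16.4 and the twice-yearly review of endpoint problems in 16.51 give the team occasions to reconsider them.

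**Conclusion.** No change to the plan is called for. This is a gap in wording that an analyst following 7.11, 16.11, 16.311 and 16.41 would fill in one way: report a test of brentuximab vedotin alone at the final level, report the level 1 responses separately, and make no claim about the combination from the decision rule.

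The gap is conditional. If level 1 is retained, nothing is affected. If it is left, the analysis population is fully specified, the type I error remains 0.097 at a true 65%, and the cut-offs, interim stop and maximum of 56 evaluable patients are unchanged. Added text would alter the label on the result and no computed quantity.

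The conclusion assumes that the report names the final dose level, as 16.11 and 16.311 imply by keeping levels apart. It does not depend on the assumed DLT rates, which govern only how often the branch arises. No view is taken on the dose levels or on whether accrual should proceed at them.
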